10.1.2 Vital Signs

The following vital signs will be collected at every in-person visit, using the given units:

- Heart rate (beats per minute)
- Systolic blood pressure (mmHg)
- Diastolic blood pressure (mmHg)
- Respiratory rate (breaths per minute)
- Body temperature (Celsius)
- Body Weight (kg)

Vital signs will be summarized with continuous descriptive statistics at each visit by treatment group. Change from Baseline will also be summarized to each post-Baseline Visit, and at hour 1, 2, 3, 4, 5, 6, 16, 22, (30, 42, 46, and 48 for subjects treated under the original Protocol at the Transplantation Visit), and (28, 40 and 44-72 for subjects treated under Amendment 1 of the Protocol at the Transplantation Visit) post-transplantation at the Transplantation Visit.

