6.9.1.1. Safety

The primary endpoint of the trial is the safety of MSC-NTF transplantation by IT and IM routes in participants with ALS

Safety will be assessed based on the incidence of treatment-emergent adverse events (TEAEs) (including serious adverse events [SAEs]) including clinically relevant changes in vital signs, clinical laboratory assessments, physical and neurological examinations, and electrocardiogram (ECG) tests.

6.9.2. Secondary Endpoints:

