7.2 Efficacy Endpoints

The efficacy endpoints are the following:

- Revised ALS Functional Rating Scale (ALSFRS-R)
- Slow Vital Capacity (SVC) (as a percent of normal)

[REDACTED]

[REDACTED]

[REDACTED]

[REDACTED]

[REDACTED]

[REDACTED]

8. General Considerations

Summaries for continuous variables will include the sample size, mean, standard deviation, median, minimum, and maximum. Minima and maxima will be reported with the same precision as the raw values; means, standard deviations, and medians will be presented to one additional decimal place than reported in the raw values. Summaries for discrete variables will include frequencies and percentages. All percentages will be rounded to one decimal place (i.e., XX.X%). Differences between treatment groups will be calculated as active – placebo and change from Baseline will be calculated as post-treatment – pre-treatment (OR follow-up visit – Baseline). The Baseline value will be defined as the last non-missing measure prior to initiation of investigational treatment. Additionally, for the pre-transplantation period and Transplantation Visits, change from screening summaries will be calculated as pre-transplantation period/Transplantation Visit minus screening.

All efficacy analyses will use one-sided alpha = 0.10 tests (which corresponds to a 2-sided alpha=0.20 test). The two-sided 80% lower confidence limit will be presented for which the lower bound is the 1-sided 90% confidence limit. In addition, the two-sided 90% and 95% confidence intervals around the difference between treatments as well as two-sided 95% confidence intervals around the point estimates within each treatment group will be provided. All summaries will be presented by treatment.

Statistical programming and analyses will be performed using SAS® Version 9.2 or higher.

[REDACTED]

[REDACTED]

[REDACTED]

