10.1 Safety Analyses

Safety will be assessed based on the incidence of adverse events (AEs) and clinically relevant changes in vital signs, clinical laboratory assessments (hematology, serum chemistry, and urinalysis), physical and neurological examinations, and ECG tests. Safety analyses will be based on the Safety population. Each safety parameter will be listed by subject.

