10.1.4 Clinical Laboratory Assessments

Clinical laboratory assessments include:

Hematology: red blood cell count (RBC), white blood cell (WBC with differentials) [L/H*]: WBC, neutrophils, lymphocytes][H: remaining differentials], hemoglobin (Hgb) [L/H], hematocrit (Hct), mean corpuscular volume (MCV), mean corpuscular hemoglobin (MCH), mean corpuscular hemoglobin concentration (MCHC), red blood cell distribution width, platelet count [L/H], coagulation - prothrombin time (PT) [H], partial thromboplastin time (PTT) [H], international normalized ratio (INR) [H]. Both counts and percentages will be reported for WBC differentials.

Serum chemistry: sodium (Na) [L/H], potassium (K) [L/H], chloride (Cl) [L/H], bicarbonate (HCO3) [L/H], blood urea nitrogen (BUN) [H], glucose [L/H], calcium (Ca) [L/H], magnesium (Mg) [L/H], phosphorus [L/H], total protein [L/H], triglycerides [H], total cholesterol [H], high density lipoprotein (HDL) [L], low density lipoprotein (LDL) [H], urea, creatinine [H], total bilirubin [H], aspartate aminotransferase (AST(SGOT)) [H], alanine aminotransferase (ALT(SGPT)) [H], alkaline phosphatase (ALP) [H], uric acid [H]

Urinalysis (dip-stick test): Specific gravity, pH, glucose [H], protein, ketones, blood [H]

*[L], [H], and [L/H] denote those tests that will have worst case low, high, and low & high summary respectively.

All test results and associated normal ranges from central laboratories will be reported in the standard International System of Units (SI unit). Continuous values will be summarized using descriptive statistics and categorical values, including low, normal, and high results with respect to reference ranges will be tabulated at each visit and treatment group. Change from Baseline for continuous values will be summarized using both continuous summary statistics as well as shift tables based on normal ranges at each post-Baseline visit. Shift from Baseline tables will also include shift from Baseline to the worst case post-Baseline. Boxplots will be presented for each quantitatively measured hematology, chemistry, and urinalysis analyte over time, with a separate boxplot for each treatment group.

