10.1.5 Electrocardiograms (ECG)

Heart rate (HR) in beats per minute, QT interval in milliseconds, and QTcF (Fridericia's) interval in milliseconds will be summarized using continuous descriptive statistics by treatment group at each visit. QTcF (Fridericia) will be estimated by the following :

$$\text{QTcF} = \frac{\text{QT}}{(\text{RR})^{1/3}} \quad \text{where RR=60/HR}$$

Change from Baseline to each post-Baseline visit will be also summarized by treatment group. The number and percentage of subjects with changes in QTcF from Baseline of >30 msec and >60 msec as well as the number and percentage of subjects with QTcF values >450 msec will be tabulated at each post-treatment visit.

Note that subjects treated under the original Protocol at the Transplantation Visit will have ECG assessments at 48 hours post-transplantation; subjects treated under Amendment 1 of the Protocol at the Transplantation Visit will have ECG assessments at 22 hours post-transplantation. These time points will be summarized separately.

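### SAP 10.1.2 gives vital signs continuous summaries only: no baseline category shifts, which the protocol plans, and no count by arm of subjects with a clinically relevant change

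*SAP*

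**What the plan says.** SAP 10.1 opens with "Safety will be assessed based on the incidence of adverse events (AEs) and clinically relevant changes in vital signs", and then names laboratory tests, examinations and ECG. It also says "Each safety parameter will be listed by subject".

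For vital signs, SAP 10.1.2 plans two things. The first is "Vital signs will be summarized with continuous descriptive statistics at each visit by treatment group". The second is "Change from Baseline will also be summarized to each post-Baseline Visit, and at hour 1, 2, 3, 4, 5, 6, 16, 22", followed by later hours that differ by protocol version: 30, 42, 46 and 48 under the original protocol; 28, 40 and 44-72 under Amendment 1. SAP section 8 defines the statistics: "Summaries for continuous variables will include the sample size, mean, standard deviation, median, minimum, and maximum".

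The neighbouring sections go further. SAP 10.1.3 has normal/abnormal shifts for examinations. SAP 10.1.4 tabulates low, normal and high laboratory results and adds "Shift from Baseline tables will also include shift from Baseline to the worst case post-Baseline". SAP 10.1.5 counts "The number and percentage of subjects with changes in QTcF from Baseline of >30 msec and >60 msec", and also counts QTcF values above 450 msec.

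In the protocol, the Synopsis (Safety) and 6.9.4.2 name vital signs among the safety data to be summarised. Both then plan shifts from baseline in categorised results, such as normal/abnormal or low/normal/high. Protocol 6.9.1.1 bases the primary endpoint on the incidence of treatment-emergent adverse events (TEAEs), "including clinically relevant changes in vital signs".

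**The concern.** Vital signs are read at ten scheduled times between Hour 1 and discharge at 44-72 hours after intrathecal and intramuscular injection (protocol 6.5.3.5 and Table 2). An acute reaction would be looked for there. The natural question is how many subjects in each arm had a relevant change at any time during the stay. A set of separate hourly summaries cannot answer it. Each hour is described on its own, nothing links a subject's readings across hours, and no limit says which values matter.

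At stake is the primary objective. Without a count, a between-arm statement about vital signs rests on reading the listings by eye, or on changes that investigators reported as adverse events. Protocol 6.8.1.7 tells investigators when a laboratory abnormality belongs on the adverse event form. The readable text has no matching rule for vital signs.

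**Working it through.** **1. The plan's own safety figure.** SAP section 5 states a 95% probability of seeing an event with a true rate of 8% among 36 MSC-NTF subjects. Check: 1 − 0.92^36 = 0.950. It reproduces. The argument is about the number of subjects affected, which is the quantity that 10.1.2 does not produce.

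**2. Categorical output by safety domain.**

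| Domain | Protocol 6.9.4.2 | SAP |
|---|---|---|
| Examinations | in the list for category shifts | normal/abnormal shifts (10.1.3) |
| Laboratory | in the list for category shifts | low/normal/high tables, shifts, worst case (10.1.4) |
| ECG | named in the Synopsis list only | QTcF threshold counts (10.1.5) |
| Vital signs | in the list for category shifts | none (10.1.2) |

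**3. What the planned statistics would show.** The documents give no size or spread for vital-sign changes, so these inputs are assumptions: a rise of 1.5-2.0 °C with SD 0.3-0.5 °C, or a systolic rise of 30-40 mmHg with SD 10-20 mmHg, in 5 of 36 active subjects. They are illustrations, not proposed limits.

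- Shift in the mean if all five occur at one hour: (5/36) × rise. This gives 0.21-0.28 °C, or 4.2-5.6 mmHg. Spread evenly over ten hours, each hourly mean moves one tenth of that.
- SD at that hour: √(s² + f(1−f)d²) with f = 5/36. For d = 2.0 and s = 0.4: √(0.16 + 0.1196 × 4) = 0.80 °C, double the SD without excursions.
- Maximum at that hour, from a simulation of 20,000 runs with independent normal changes and n = 36. The entry is the share of runs in which the maximum exceeds the 95th percentile of the maximum without excursions.

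| Assumed rise, SD | 5 subjects affected at the hour | 1 subject affected at the hour |
|---|---|---|
| 2.0 °C, 0.4 | about 100% | 98% |
| 1.5 °C, 0.5 | 97% | 53% |
| 40 mmHg, 15 | 91% | 41% |
| 30 mmHg, 15 | 61% | 21% |
| 30 mmHg, 20 | 33% | 11% |

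So a fever usually shows in the maximum, and a pressure excursion often does not. In neither case does the table give the number of subjects.

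**4. Are hourly maxima comparable between arms?** With no effect and exchangeable subjects, the larger maximum falls in the active arm with probability 36/48 = 75%. For normal data the expected maximum is 2.12 SD with n = 36 and 1.63 SD with n = 12. The gap of 0.49 SD is 0.20 °C at SD 0.4, or 7.3 mmHg at SD 15, and comes from arm size alone.

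**5. What a count would give.** Suppose 5 of 36 and 0 of 12 subjects cross a limit. The proportions are 13.9% (exact 95% interval 4.7-29.5%) and 0% (0-26.5%), with two-sided Fisher p = 0.31. That is descriptive information with its uncertainty shown, not a test result.

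**The case against.** Four stronger readings are tempting, and the documents do not support them.

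- **A reader might infer that only arm means are produced.** SAP section 8 adds the SD, median, minimum and maximum.
- **A reader might infer that a brief excursion would vanish from the report.** The maximum and SD often show a fever (working, step 3), every value is listed by subject, and the study has only 48 treated subjects.
- **A reader might infer that SAP 10.1 and 10.1.2 contradict each other.** In 10.1, incidence may govern adverse events alone. Protocol 6.9.1.1 lets relevant changes enter through TEAEs, which SAP 10.1.1 tabulates by arm. The adverse event definition in protocol 6.8.1.1 covers any unfavourable sign, and Table 2 schedules adverse event review at each post-transplant reading.
- **A reader might infer that the category shifts were dropped without record.** No readable item in SAP section 13 mentions them, but three items there are redacted, so this cannot be settled.

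It can also be argued that the protocol's shift sentence was not meant for every item in its list, since the list includes concomitant medications, for which a shift makes little sense. That leaves some doubt about intent. Vital signs do lend themselves to low/normal/high categories, though, and the absence of a count does not depend on that sentence.

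The split of late hours by protocol version is also a limited matter: it affects only hours after 22, and the documents do not say how many subjects fall under each version.

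What remains is narrower. A listing is not a comparison between arms, an hourly maximum is one value from one subject, and the adverse event route depends on investigator judgement with no stated rule for vital signs.

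**Conclusion.** The point holds as a gap in the planned output. SAP 10.1.2 omits the baseline category shifts that the protocol plans for a list including vital signs. No planned vital-sign table gives the number of subjects per arm with a clinically relevant change, a term the readable text does not define for vital signs. Extreme values remain visible through the maxima, the listings and the TEAE tables, so this is a weakness in summarising the primary objective, not a loss of data.

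The 75% figure needs only the arm sizes and exchangeability under no effect. The expected maxima also assume normal data. The detection percentages rest on assumed excursions and SDs and should be read as a range: 53-98% for temperature and 11-41% for systolic pressure when one subject is affected at an hour.

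**What to change.** In SAP 10.1.2:

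1. Restore the protocol's shift table for vital signs, from baseline to each post-baseline visit, using categories that the sponsor defines.
2. Add one table by arm with the number and percentage of subjects whose worst value falls outside limits that the sponsor fixes before unblinding. Cover temperature, blood pressure, heart rate and respiratory rate. Show two windows, Hour 0 to discharge and through Week 24. Give exact 95% intervals and label the table descriptive.

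Taking the worst value over the inpatient stay pools the two protocol versions in one table. A footnote should say that the versions differ in the late reading times, because more readings give more chances of an extreme. If the shifts were left out on purpose, section 13 should say so.

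The cost is the shift table, one further table from data already collected, and agreement on limits before unblinding. With 12 placebo subjects the intervals will be wide, and the table should not be presented as evidence of no difference.

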10.1.3 Physical and Neurological Examinations

The physical and neurological examination results, graded as normal or abnormal will be summarized using counts and percentages at each visit. Shifts from Baseline (normal vs. abnormal) for physical examination and neurological exam will be summarized to each post-Baseline visit using counts and percentages. Note that subjects treated under the original Protocol at the Transplantation Visit will have a physical exam assessment at 42 hours post-transplantation; subjects treated under Amendment 1 of the Protocol at the Transplantation Visit will have a physical exam assessment at 40 hours post-transplantation. The 40 hour and 42 hour time points will be summarized together.

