6.4.1. Inclusion Criteria

Study subjects meeting all of the following criteria will be allowed to enroll in the study:

1. Males and females ages 18 to 75 years old, inclusive.

2. ALS diagnosed as possible, laboratory-supported probable, probable, or definite as defined by revised El Escorial criteria.
3. Disease onset, as defined by first reported occurrence of symptomatic weakness, spasticity, or bulbar symptoms, of more than 12 months and less than or equal to 24 months.
4. Current disease symptoms must include limb weakness.
5. ALSFRS-R ≥ 30 at the Screening Visit.
6. Upright slow vital capacity (SVC) measure $\geq 65\%$ of predicted for gender, height, and age at the Screening Visit.
7. Subjects must be taking a stable dose of riluzole for at least 30 days prior to enrolment or not be on riluzole, and not have been on it for at least 30 days prior to enrolment (riluzole-naïve subjects are permitted in the study).
8. Capable of providing informed consent and willing and able to follow study procedures, including willingness to undergo lumbar puncture.
9. Geographic accessibility to the study site and willingness and ability to comply with follow-up.
10. Women of child-bearing potential must agree not to become pregnant for the duration of the study. Women must be willing to consistently use two forms of contraceptive therapy throughout the course of the trial, and undergo a pregnancy test one week before bone marrow aspiration. Men must be willing to consistently use two forms of contraceptive if their partners are of child-bearing age.
11. Citizen or permanent resident of the United States.

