6.9.4.2. Safety analyses

Primary Objective: The safety of MSC-NTF transplantation via combined IT and IM injection in participants with ALS is the primary objective of this study. Safety endpoints include AEs, changes in physical and neurological examination findings, hematology, serum chemistry, urinalysis, vital signs, and requirement of concomitant medications.

All AEs will be coded to System Organ Class (SOC) and Preferred Term (PT) using the MedDRA®. The number of Treatment-Emergent Adverse Events (TEAEs) and the number of subjects with any TEAEs (along with percentages) will be tabulated by SOC and PT within each SOC by treatment group and over treatment groups. To count the number of subjects with any TEAEs, a subject who experiences multiple TEAEs within the same SOC will be counted only once for that SOC (whether or not the TEAEs are coded to the same PT). A subject who experiences multiple TEAEs coded to the same PT within the same SOC will be counted only once for that particular PT. In the summary, SOC will be listed in ascending alphabetical order; PTs will be listed in order of descending frequency for all subjects within each SOC.

Separate summaries will be provided for the following categories of AEs:

- TEAEs
- TEAEs by severity
- Treatment-related TEAEs
- Serious TEAEs

The proportion of subjects having each AE will be compared between treatment using Fisher's exact tests.

When evaluating changes in safety parameters, baseline will be defined as the last measurement prior to transplantation (i.e., prior to treatment).

Physical examination, neurological examination, hematology, serum chemistry, vital signs and concomitant medications will be summarized using descriptive statistics (n, mean, standard deviation, median, minimum, and maximum) if the data is continuous and using counts and percentages if the data is discrete. Shifts from baseline in categorization of results (e.g. normal/abnormal or low/normal/high) will also be summarized.

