5 Blood Biochemistry: Na, K, Cl, HCO₃, BUN, Cr, Glucose, Ca, Mg, Phosphorus, total protein, triglycerides (TG), Total cholesterol, HDL, LDL, urea, creatinine, total bilirubin, AST(GOT), ALT(GPT), ALP - Time Window: +/- 2 hours

6 Urinalysis (dip-stick test) - Specific Gravity, pH, glucose, protein, ketones, blood

7 Coagulation PT, PTT

8 Can be done prior to discharge

4. Study Treatment

The investigational products for this study will be

- MSC-NTF cells
- Placebo (Dulbecco Modified Eagle Medium, DMEM)

IT Transplant Procedure: Participants will undergo a lumbar puncture (Spinal needle 20GA 3.50 IN (0.9 x 90 mm)) followed by intrathecal injection of cells or placebo (DMEM).

IM Transplant Procedure: Participants will undergo a unilateral (right) IM transplantation of cells or placebo solution (DMEM) into 24 sites in the upper arm.

The study flowchart described above is shown in Figure 2.

[figure not shown]

Figure 2: Study Groups Flowchart

5. Sample Size

This is a Phase II study for which no formal sample size calculation has been performed. The sample size chosen was not based on statistical considerations. The total of 36 treatment and 12 placebo subjects are expected to be a sufficient number to obtain adequate characterization of common treatment emergent adverse events and to observe trends for treatment effects on the efficacy measures chosen for this study. Additionally, with 36 subjects in the MSC-NTF treatment group, the study has 95% probability of seeing adverse events that occur at a true rate of 8% or greater. Therefore, if an adverse event of a specific type does not occur, there is 95% probability that the true rate of the adverse event is less than 8%.

6. Analysis Populations

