8.2 Study Baseline

Baseline demographics and disease characteristics (sex, age, race, ethnicity, El Escorial Criteria, ALS medical history) are collected from Screening Visit (V1). [REDACTED]

[REDACTED] are defined as the last non-missing values prior to transplantation. Baseline measures for safety variables are defined as the last non-missing measurement prior to transplantation.

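### The normal/abnormal shift table for the neurological examination cannot show worsening of an already abnormal finding and, unless components are graded separately, can show almost no new deficit

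*SAP*

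**What the plan says.** Protocol 6.9.4.2 makes safety the primary objective and states: "Safety endpoints include AEs, changes in physical and neurological examination findings". SAP 7.1 lists the neurological examination separately among the safety endpoints.

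SAP 10.1.3 sets the scale: "The physical and neurological examination results, graded as normal or abnormal will be summarized using counts and percentages at each visit". The only comparison over time is: "Shifts from Baseline (normal vs. abnormal) for physical examination and neurological exam will be summarized to each post-Baseline visit using counts and percentages". Protocol 6.9.4.2 plans the same kind of table: "Shifts from baseline in categorization of results (e.g. normal/abnormal or low/normal/high) will also be summarized". Neither text defines a category for a worsened or a new finding, and neither says whether the grade applies to the whole examination or to each component.

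The reference point is given in SAP 8.2: "Baseline measures for safety variables are defined as the last non-missing measurement prior to transplantation". Protocol 6.5.3.5 schedules a neurological examination at Visit 5 before the injections, so Baseline will normally be that examination, after the 12-16 week run-in.

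El Escorial-defined ALS is an entry requirement (Protocol 6.4.1, criterion 2), and criterion 4 adds: "Current disease symptoms must include limb weakness".

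**The concern.** A shift table carries information only about patients who can move between its categories. In a progressive motor disease with weakness required at entry, the overall neurological examination will be abnormal at Baseline in nearly everyone and will stay abnormal. If one grade covers the whole examination, a new sensory, radicular, sphincter or cranial-nerve sign after intrathecal injection lands in the same abnormal-to-abnormal cell as unchanged ALS. If components are graded separately, that problem remains for each component the disease already affects, the motor component above all.

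At stake is how the table will be read. It belongs to the primary objective of a trial of an intrathecal cell product. Two arms that both stay abnormal would look like evidence of no neurological change, when the table may have had little or no capacity to show any.

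**Working it through.** **Inputs**
- Arm sizes: 36 active, 12 placebo (Protocol 6.9.4.4; SAP Section 5).
- Scale: two categories, grading unit not stated (SAP 10.1.3).
- Baseline: last value before transplantation (SAP 8.2).
- Entry: ALS with limb weakness (Protocol 6.4.1).
- The only detection figure in the documents is in SAP Section 5: "the study has 95% probability of seeing adverse events that occur at a true rate of 8% or greater". It refers to 36 active patients and to adverse events, not to the examination table.

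**1. Reproduce the plan's figure.** The probability of at least one event is 1 − (1 − p)^n. With p = 0.08 and n = 36, 1 − 0.92^36 = 0.950. In the other direction, the one-sided 95% upper limit after 0 of 36 events is 1 − 0.05^(1/36) = 0.0798, or 8%. The stated figure is correct for adverse events.

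**2. What each kind of change does in the table**

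| Status at Baseline | What happens after transplant | Cell filled |
|---|---|---|
| Normal | New deficit | Normal to abnormal (visible) |
| Abnormal | Unchanged | Abnormal to abnormal |
| Abnormal | Existing finding worsens | Abnormal to abnormal |
| Abnormal (overall grade) | New deficit elsewhere | Abnormal to abnormal |

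The last three rows cannot be told apart. The third row holds for any grading unit. The fourth arises only under one overall grade.

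**3. Size under one overall grade.** Only the m patients graded normal at Baseline can shift, so the chance that the table shows at least one new deficit is 1 − (1 − p)^m. If all are abnormal, m = 0 in each arm and the probability is 1 − (1 − p)^0 = 0 for every p.

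**4. Range if some patients are graded normal.** The documents give no Baseline grades, so the share normal is an assumption. For the active arm with p = 0.08, taking new deficits to be equally likely whatever the Baseline grade:

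| Share normal | m of 36 | 1 − 0.92^m | True rate needed for 95% |
|---|---|---|---|
| 0% | 0 | 0% | none suffices |
| 10% | 4 | 28% | 53% |
| 25% | 9 | 53% | 28% |
| 50% | 18 | 78% | 15% |
| 75% | 27 | 89% | 11% |
| 100% | 36 | 95% | 8% |

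The last column is 1 − 0.05^(1/m). The lower rows are plausible only for a separately graded component that ALS usually leaves normal, such as sensation. The top row is the expected case for an overall grade, and the motor component would lie at or near it.

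**5. Compare with neighbouring sections.** SAP 10.1.4 adds a shift to the worst post-Baseline value for laboratory tests, and SAP Section 11 adds a shift to the worst post-treatment suicidal-ideation score. SAP 10.1.3 has neither a worst-value shift nor a category for worsening.

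**The case against.** A reader might infer that new neurological harm cannot appear in this table at all, that it would reach the report only if an investigator chose to record an adverse event, or that the plan makes no comparison with the pre-transplant examination. The documents do not support these readings.

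- **Grading unit.** It is not stated and the CRF is not in the documents. With component grades, a new sensory or cranial-nerve sign in a component normal at Baseline would shift. The figure of 0 is conditional on one overall grade.
- **Baseline.** SAP 8.2 together with Protocol 6.5.3.5 already makes the pre-transplant examination the comparator. What is missing is a category for new or worse.
- **Other routes.** Protocol 6.9.1.1 assesses safety through treatment-emergent events, "including clinically relevant changes in vital signs, clinical laboratory assessments, physical and neurological examinations". Protocol 6.8.1.1 defines an adverse event to include any unfavourable sign, whatever its cause. SAP 10.1.1 counts worsening after transplantation as treatment-emergent, and SAP 10.1 lists every safety parameter by subject. The 95% figure in SAP Section 5 holds for a deficit recorded as an adverse event.
- **Efficacy scales.** ALSFRS-R and SVC measure functional and respiratory decline by arm.
- **Inference about Baseline.** Criterion 4 concerns symptoms. An abnormal examination in every patient is very likely but is not documented.

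All of this stands, and it limits the point to the examination table. It does not make the table informative. Protocol 6.8.1.7 says when a laboratory abnormality goes on the adverse-event form; the visible text has no such rule for examination findings, so capture relies on judgement against a background of progressing ALS. The worsening rule applies to an event already recorded as an adverse event. Listings do not compare arms and, if the field is binary, would read abnormal throughout. The ALSFRS-R items in SAP Table 3 include no sensory or sphincter item.

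**Conclusion.** The point holds for the table, not for neurological safety reporting as a whole. As written, the shift in SAP 10.1.3 cannot show worsening of a finding already abnormal, whatever the grading unit. Unless components are graded separately, it can show almost no new deficit either: 0 of 36 active and 0 of 12 placebo patients could shift if all are abnormal at Baseline. For an 8% rate of new deficits in the active arm, the table's chance of showing any runs from 0% to 95% depending on the share graded normal, and the plan leaves undecided where in that range it falls.

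This rests on two assumptions: that limb weakness at entry means an abnormal examination at Baseline, and, for the figure of 0, that there is a single overall grade. Adverse-event tables and listings remain as separate routes. The change is a worthwhile, low-cost improvement to one descriptive table under the primary objective. An unchanged table should not be cited as reassurance.

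**What to change.** In SAP 10.1.3:

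1. State whether the examination is graded overall or by component.
2. Tabulate shifts by component (for example mental status, cranial nerves, motor, sensory, reflexes, coordination and gait), with patients normal in that component at Baseline as the denominator.
3. Add a count of patients with a new or worsened finding since the pre-transplant Visit 5 examination, by arm and visit and as worst post-Baseline, as SAP 10.1.4 does for laboratory tests.
4. Use recorded component grades where they exist. Where only free text exists, have the blinded medical monitor code new or worsened findings before unblinding. Protocol 6.3.4 makes the Medical Monitor the source of emergency codes, so the coding must be done without opening them.

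**Cost.** One extra table and some blinded coding. No visit or procedure is added, since the examination is already scheduled at Visits 5 to 10. The table can use only what the CRF captured. SAP 6.3 shows that this version follows the blinded data review, so a new CRF field would help only for visits not yet completed. ALS progression will also produce worsened findings in both arms, so the added count has to be read against the 12 placebo patients and will be imprecise.
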